#### INSTRUCTIONS

This template is intended to help investigators prepare a protocol that includes all of the necessary information needed by the IRB to determine whether a study meets approval criteria. **Read the following instructions before proceeding:** 

- 1. Use this protocol template for a PI initiated study that includes direct interactions with research subjects. Additional templates for other types of research protocols are available in the system Library:
  - If the study involves genetic testing, blood draws, or MRIs, do not use this form. Use the biomedical protocol template.
  - If the study involves secondary analysis of data, use the Secondary Analysis of Data protocol.
  - For activities that may qualify as exempt research, use the Request for Exemption form (which includes a decision tree to determine whether or not your study qualifies as exempt).
- 2. If a section or question does not apply to your research study, type "Not Applicable" underneath.
- 3. Once completed, upload your protocol in the "Basic Information" screen in IRES IRB system.

#### Glossary of Acronyms

IPV	Intimate Partner Violence
СМ	Child Maltreatment
PFDP	Parent and Family Development Program
UCONN	University of Connecticut
F4C	Fathers for Change

BIP	Batterer Intervention Program
RF	Reflective Functioning
ER	Emotion Regulation

# SECTION I: GENERAL INFORMATION

1. **Probable Duration of Project:** State the expected duration of the project, including all follow-up and data analysis activities.

# 9 years (for both Phases I and II)

2. **Study location:** State where the study will take place and in what setting.

Yale University Child Study Center and the Department of Psychiatry will be the locations for this research study. Participants may I be recruited, consented, assessed and receive study treatments at the Parent and Family Development Program (PFDP) Clinic at [name], a licensed adult and child mental health clinic on the Yale School of Medicine Campus or via Zoom secure conferencing is in person meetings are not feasible.

If international, complete and submit International checklist (http://your.yale.edu/policies-procedures/forms/450-ch-1-international-research-checklist) Note: If your research involves interactions with any embargoed countries you should contact the Director of Corporate Contracts and Export Control Licensing ([contact] or call [contact]) for guidance on how to proceed.

3. Help us categorize your research. Are you using any of the following?

- Class Project
- □ Participant Observation
- $\boxtimes$  Interviews
- 🛛 Surveys
- □ Focus groups (study is not anonymous)
- □ Research in K-12 schools (submit a School Agreement form for the study)
- □ Deception (submit a Debriefing sheet)
- Audiotaping, videotaping or photography of individuals (study is not anonymous)
- □ Public viewing of videotapes or photographs
- □ Yale Psychology Pool (study does not qualify for exemption)
- □ International research sites (attach the International Checklist)
- □ Online (web-based) activities
- □ Social networks

# SECTION IV: RESEARCH PLAN

1. **Statement of Purpose:** State the scientific aim(s) of the study, or the hypotheses to be tested.

This project proposes to conduct important Stage I and Stage II treatment development steps to test the efficacy of Fathers for Change (F4C) compared to Batterer Intervention Program (BIP).

# Aims for Phase I:

- 1. Develop a revised BIP manual for individual treatment delivery as a comparison treatment.
- 2. Develop a fidelity measure to distinguish F4C from BIP for therapist fidelity coding.
- 3. Establish acceptability and feasibility of F4C compared to traditional group BIP (BIP-G) and an individually delivered BIP (developed in aim 1 above; BIP-I). We will test the following specific research hypotheses:
  - i. Fathers randomized to F4C will have higher completion rates than those in either the BIP-I or BIP-G treatments.
  - ii. Fathers will report greater working alliance and satisfaction with F4C than either BIP condition
- 4. Assess initial intervention signal of F4C compared with BIP-I (developed in aim 1 above) and a group format BIP-G (current standard of care) program of comparable length. We will test the following specific research hypotheses:
  - i. Fathers receiving F4C will evidence greater improvement in reflective functioning (RF) and emotion regulation post-intervention compared to fathers receiving BIP-I or BIP-G.
  - ii. Fathers receiving F4C will show greater reductions in intimate partner violence (IPV) and child maltreatment (CM) over the 18 weeks of treatment compared to fathers receiving either BIP condition.
  - iii. Fathers receiving F4C will maintain reductions in IPV and CM in the 3 months following treatment.

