The RA will complete study assessments in person or via zoom with fathers, mothers and partners at baseline, immediately following intervention completion, at 6 and 12 month follow-ups. Each measure and timing of assessment are outlined in Table 1.

Table 1. Assessment	Rater	Baseline	Weekly During	Monthly During	Post- intervention	6& 12 Month- FU
Schedule			Intervention	Intervention		_
ir v Out comes						
Family Socialization Interview Revised (FSI-R)  – IPV module	Masked Coder	X			X	Х
Time-line follow-back for IPV (56, 57)	Father, Mother, Current Intimate Partner		Х			
Abusive Behavior Inventory (ABI)	Father, Mother, Current Intimate Partner	X			X	X
Court and Arrest Records	N/A	X				Х
Child Maltreatment and Parenting Outcomes						
Child Protective Services Records	N/A	X				X
Family Socialization Interview Revised (FSI-R)  – Parenting Risk module	Masked Coder	x			X	X
Timeline Followback-CM Risk	Father and Mother		х			
Conflict Tactics Scale-Parent Child	Father and Mother	x			x	X
Father-Child Free Play coded using Child Interactive Behavior Rating (CIB)+	Masked Coders	X			X	X (12 month only)
Children's Emotions Scale (RCES)	Mother and Father					
Brief Infant Toddler Social Emotional Assessment (BITSEA) Trauma Symptom Checklist for Young Children (TSCYC) or Trauma symptom checklist for children (TSCC) appropriate for child age	Mother and Father Children >7-Self Report	X			X	X
Kiddie Diagnostic Interview Schedule PTSD Module OR Diagnostic Infant and Preschool Assessment (DIPA) modified PTSD module	Mother and Father	X			x	x
Satisfaction Outcomes						
Client Satisfaction Questionnaire 8 (58)	Father				Х	
Intervention Targets (Mechanisms)						
Unified Protocol Skill Use Scale (UPSUS)122 and select items from the 28-item Brief COPE	Father		X			
Difficulties in Emotion Regulation Scale (59) DERS Short Form	Father	X	Х		x	Х
Reflective Functioning Questionnaire-8 (RFQ)(60)	Father	X	Х			
Parent Reflective Function Questionnaire (PRFQ) (61)	Father	X	X			
Intervention Process Variables						
Working Alliance Inventory (62)	Father and Clinician			Х		
CHANGE Coding	Trained Reliable Coders			Х		
Motivation to Change	Father			Х		

	1			1	1
Therapist Session Report Form	Clinician		x		
Other variables to classify the sample					
STRESS Trauma History and PTSD Scale	Father	Х			
Alcohol Use Disorders identification Test (AUDIT) – Self report(66)	Father	Х			
Drug Abuse Screening Test- 10 (DAST- 10)(67)	Father	Х			

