# Measures during baseline

**Child Maltreatment Risk:** We will collect official records of child maltreatment from the Department of Children and Families. We will also collect logs of child maltreatment risk behaviors (harsh discipline and hostility toward the child) as reported on time line follow-back calendars during treatment. Parents will report on their harsh/hostile behavior on the Conflict Tactics Scale-Parent Child Version. These will be used to inform masked coder ratings on the Family Socialization Interview (FSI-R; our primary outcome measure). The FSI-R assesses severity of child maltreatment risk based on a compilation of data from self- report, collateral reports and records.

**Parent-Child Interaction Tasks**. Each Father-child dyad is video-taped in a semi-structured 20-minute play session. It consists of 15 minutes of free-play and a 5-minute clean-up. Each play session will be coded using the Child Interactive Behavior Coding which has been validated with children aged birth to 13 years. Infant, Preschool or Child coding guidelines will be used depending on child age. The following codes are used across ages: 1) parental hostility/intrusiveness, 2) dyadic reciprocity, and 3) child's relationship behavior toward the parent (avoidance, anxiety). Parents and children will be rated by trained blind coders who have attained .75 reliability to the task author [name]; 15% of the tapes will be double coded for reliability checks. The video recording of play assessments with the child pre and post treatment is necessary for coding father-child interactions before and after the treatment.

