# Weekly and Monthly Measures During Treatment

The RA will meet with fathers via password protected zoom link or in person to complete logs of IPV, substance use and interactions with their children and monthly assessments of working alliance and treatment motivation via computerized survey at the time of their weekly clinical appointment. If fathers do not show for their appointment RAs will phone him to collect the information or email a secure survey. All data will be entered into a secure web-based REDCap database.

**TimeLine Follow-back-Spousal Violence, Child Maltreatment Risk, & Substance Use (TLFB-SV/SU/CM)** will be used to assess specific types of IPV (physical, sexual, psychological) toward partners on any given day, contact with the target child and child maltreatment risk behaviors (yelling, swearing, spanking, slapping, ignoring, harsh punishment). The TLFB-SV/SU/CM will be administered weekly to assess violence, substance use and CM risk behaviors during treatment. This is a reliable and valid instrument that has been used to assess relationship violence over time and links to substance use.  Participants, *the mother of their youngest child and if different their current female partner* will be asked to report IPV and CM throughout treatment.

**Measures of Treatment Targets:** Fathers will complete items from the Parental Acceptance Rejection Questionnaire, COPES and Unified Protocol Skill Use Scale to assess intervention coping skill use and emotion regulation/RF changes during treatment.

**Measures of Treatment Process:** Fathers will complete the **Working Alliance Inventory**,  **Motivation to Change** (85) on a monthly basis and the **Client Satisfaction Questionnaire** at the end of treatment to document (a) the quality of their relationship with their clinician, (b) their perceived motivation for change, and (c) satisfaction with treatment.

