# Analytic Plan.

We will use Research Electronic Data Capture (REDCap™), a widely used secure web-based software package designed for clinical trials to collect study data.

Preliminary Analysis: A series of preliminary analyses will be conducted to: (1) characterize the sample, (2) document the internal reliability of measures, (3) check for logical consistency among related variables, (4) identify outlying values that should be considered for truncation, and (5) assess whether there are significant differences in outcomes based on study therapist. Although urn randomization procedures will be used to balance distribution of specific characteristics across treatment groups, we will explore between-group differences in urn variables and other demographics and possible moderators. Data analyses will be done independently and without

knowledge of group assignment, with the participant's group assignment anonymized to "treatment 1" or "treatment 2".

Phase I Hypotheses:

- i. Fathers randomized to F4C will have higher completion rates than those in the BIP-I or BIP-G treatment. Chi-square analysis will be used to examine between group differences in treatment completion.
- ii. Fathers will report greater working alliance and satisfaction with F4C than BIP-I or BIP-G. Analysis of variance will be used to test between group differences in working alliance and client satisfaction.
- iii. Fathers receiving F4C will evidence greater improvement in RF and emotion regulation, IPV, and child maltreatment(CM) compared with fathers receiving BIP-I or BIP-G postintervention. Mixed effects regression will be used to test for between-group differences in RF, emotion regulation, IPV, and CM representing treatment effects associated with F4C versus BIP over time. Separate IPV and CM sum scores will be created. Any instance of IPV or CM by any report (self, co-parent or current partner report on the Timeline Follow Back, child protection or arrest records) will be counted to create a sum score across reports. The Child Interactive Behavior Codes of Intrusiveness and Child Avoidance will be used as our observational measures of CM risk. Total coded RF score as measured by the PDI and self-reported emotion regulation on the DERS will be used to test impact mechanisms of F4C.

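### Phase I hypothesis 4.iii cannot be tested as written, because its outcome score has no self or partner report for the 3 months after treatment; separately, the sources behind the FSI-R child maltreatment risk rating differ by wave

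*Combined protocol and SAP*

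**What the plan says.** **Hypotheses.** Under Aims for Phase I, aim 4, hypothesis ii expects larger falls in IPV and CM with F4C "over the 18 weeks of treatment compared to fathers receiving either BIP condition". Hypothesis iii then states that "Fathers receiving F4C will maintain reductions in IPV and CM in the 3 months following treatment".

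**Outcome.** Analytic Plan, Phase I Hypotheses, item iii, builds separate IPV and CM sum scores. It counts incidents from "self, co-parent or current partner report on the Timeline Follow Back, child protection or arrest records" and analyses them by mixed effects regression over time.

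**When the Follow-Back is given.** Weekly and Monthly Measures During Treatment says: "The TLFB-SV/SU/CM will be administered weekly to assess violence, substance use and CM risk behaviors during treatment". Fathers, mothers and current partners "will be asked to report IPV and CM throughout treatment". In Table 1, both Follow-Back rows (IPV and CM risk) carry a mark only in the weekly column for the intervention period.

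**Records.** Section VI, item 3, asks the state agency for the number of reports and arrests over 26 weeks of treatment. Hypothesis 4.ii and the Treatment Phase section give 18 weeks. Table 1 marks court, arrest and child protection records at baseline and at 6 and 12 months, but not at post-treatment.

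**Visits.** Assessments take place at "baseline, immediately following intervention completion, at 6 and 12 month follow-ups". The Follow-up section and the payment list in Section VIII agree.

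**FSI-R.** Measures during baseline, under Child Maltreatment Risk, lists official records, the Follow-Back logs kept during treatment, and the Conflict Tactics Scale-Parent Child (CTS-PC). It then says: "These will be used to inform masked coder ratings on the Family Socialization Interview (FSI-R; our primary outcome measure".

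**The concern.** A claim that reductions are maintained needs the same quantity measured during treatment and again over the stated later period. The Phase I score depends on the Follow-Back for everything that fathers, mothers and partners report, and the Follow-Back stops when treatment stops. If nothing changes, 4.iii will be left unanswered, answered from official records alone, or answered on a different instrument chosen after the fact.

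The second issue concerns the measure that the protocol calls primary. Phase II compares trajectories across baseline, post-treatment, 6 and 12 months. If coders rate child maltreatment risk from one set of sources at one wave and another set at the next, part of the apparent change may be a change in what the coder could see.

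**Working it through.** There is no stated figure to reproduce. The check sets instruments against time points, with some week arithmetic.

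**1. The window of 4.iii.** Take treatment as weeks 1 to 18 and 3 months as 13 weeks.
- End of window: 18 + 13 = week 31, so the window is weeks 19 to 31.
- Follow-Back coverage is weeks 1 to 18, so it overlaps 0 of 13 weeks.
- Records counted over 26 weeks from treatment start reach 26 − 18 = 8 weeks past treatment and stop 31 − 26 = 5 weeks short. They are requested as a total for the period, so those 8 weeks could not be separated from the treatment weeks.
- If 26 weeks is instead the length of treatment, the records window ends with treatment and overlaps none of the following 13 weeks.

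On either reading, the score as defined does not cover the period named in 4.iii. Item iii of the analytic plan is also worded for the post-intervention comparison, and no separate analysis is given for 4.iii.

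**2. Coverage by instrument (Table 1).**

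| Instrument | Baseline | Treatment weeks | Post | 3 months | 6 and 12 months |
|---|---|---|---|---|---|
| Follow-Back, IPV and CM | no | weekly | no | no | no |
| Abusive Behavior Inventory (ABI) | yes | no | yes | no | yes |
| CTS-PC | yes | no | yes | no | yes |
| FSI-R, both modules | yes | no | yes | no | yes |
| Court, arrest and child protection records | yes | no | no | no | yes |

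The column for 3 months is empty. The ABI, CTS-PC and FSI-R do allow change from baseline on one instrument, but they are not part of the Phase I score.

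**3. Hypothesis 4.ii.** Its wording concerns the treatment weeks. Weekly Follow-Back reports in a mixed model give a slope per arm, and randomised arms can be compared on that slope without a pre-treatment value. What is missing is only the level before week 1.

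**4. Sources named for the FSI-R child maltreatment risk rating.**

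| Source | Baseline | Post | 6 and 12 months |
|---|---|---|---|
| Follow-Back logs | none | up to 18 weekly logs per informant | none |
| CTS-PC | yes | yes | yes |
| Official records | marked | not marked | marked |

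Post-treatment gains the logs and, on Table 1, loses the records. Only the CTS-PC is common to all waves. No instruction tells coders how to handle the difference.

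**The case against.** The strongest reply is that Table 1 looks like the Phase II schedule. It has 6- and 12-month visits and session coding, and it omits the interview from which Phase I takes its coded reflective functioning score. A Phase I schedule might have had a 3-month contact. That is fair, but the document gives no other schedule, and the text on the Follow-Back independently confines it to treatment. As it stands, nothing supports 4.iii.

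A second reply is that a records pull at 6 months, or an ABI score at 6 months, may reach back over the first 3 months. That is possible. However, the records text asks for totals over a different window, the recall period of the ABI is not given, and neither would be the score used during treatment.

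Several stronger readings are tempting but not supported:
- A reader might infer that change from baseline cannot be measured on one scale at all. The ABI, CTS-PC and both FSI-R modules are scheduled at baseline, post-treatment and both follow-ups, and the post-intervention section repeats the baseline assessments.
- A reader might infer that 4.ii fails too. It does not, for the reason in step 3.
- A reader might infer that the logs make post-treatment ascertainment denser and so hide part of the fall. Table 1 removes records at the same wave, so the net direction is unknown. A shift common to both arms would also largely cancel in the arm contrast.
- A reader might infer that the logs are more complete in one arm. Phone and email back-up, payment per log, blinded assistants and maternal reports all work against this, and no log completion rates are given.
- A reader might extend the FSI-R point to the IPV module. The sentence on sources stands under child maltreatment risk, and no equivalent covers IPV.

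**Conclusion.** The point holds in two parts.

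First, 4.iii cannot be tested as written. The Phase I score has self or partner reports for 0 of the 13 weeks, and the records window covers at most 8 of them. This assumes that the only schedule given also applies to Phase I, and that 3 months means about 13 weeks. Hypothesis 4.ii remains testable and lacks only a pre-treatment Follow-Back level.

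Second, the named sources behind the FSI-R child maltreatment risk rating differ between waves. This is a real threat to comparing waves, but the document has no figures from which to derive a direction or a size, and none is claimed here.

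The change should be made. It determines whether one stated hypothesis can be answered and how change on a primary measure can be read.

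**What to change.** 1. **State which schedule governs Phase I, then give 4.iii data or restate it.** Either add a Follow-Back look-back to interviews already held (a pre-treatment window at baseline, and the first 3 months after treatment at the 6-month interview), or restate 4.iii as an F4C-versus-BIP contrast at a scheduled follow-up on the ABI, CTS-PC and FSI-R. The restatement also supplies the comparator that the sentence lacks, although it changes the time point. If Phase I has no 6-month interview, either option needs a follow-up contact to be added.
2. **Reconcile the 18- and 26-week windows.** Have the records request cover the same periods as the assessments, including the period up to post-treatment, with a separate count for each period.
3. **Rate the primary FSI-R from the same sources and look-back at every wave.** Analyse the weekly logs separately as an on-treatment outcome, or use them in a sensitivity rating.

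**Cost.** The changes are a wording change, a coder instruction, a wider records request and, for the look-back option, slightly longer interviews. At 6 months (about week 18 + 26 = 44), the look-back asks about events 13 to 26 weeks earlier, so it is not equivalent to a weekly log. The post-treatment FSI-R rating would use less information than it could.

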# Exploratory aim Phase I:

- 5. Test whether improved RF and emotion regulation are associated with reduced IPV and CM consistent with the F4C mechanisms of change We will test the exploratory hypothesis:
  - i. RF and emotion regulation will mediate the association between treatment group and IPV and CM outcomes at follow-up.

# Aims for Phase II:

AIM 1. Compare F4C to a standard BIP in its efficacy to reduce FV by decreasing fathers' violent behavior, improve father-child interactions, and reduce child mental health symptoms. *Hypotheses.* Children of fathers who receive F4C (n=140), relative to BIP (n=140), will: (1a) experience less FV, (1b) have more positive father-child interactions, and (1c) have lower FV-related mental health symptoms (PTSD, internalizing/externalizing) at post treatment and 6- and 12-month follow-ups. The effects of both treatments on father and coparent mental health outcomes will also be examined (1d *exploratory*).

AIM 2. Identify and compare latent change profiles of therapeutic targets (RF, ER) in F4C and BIP fathers across the 18-week intervention. *Hypotheses*. Compared to BIP, more F4C fathers will show profiles of healthy change in therapeutic targets: (2a) masked coding of insession RF/ ER (i.e., increased RF and adaptive ER, decreased maladaptive ER), and (2b)

between-session self-reported RF/ ER (i.e., increased RF and adaptive ER, decreased maladaptive ER). F4C change profiles will reveal critical junctures in treatment that precipitate change, thereby serving to optimize timing/delivery of treatment components (2c, *exploratory*).

AIM 3. Examine the mediating role of therapeutic change targets (RF, ER) on child-related outcomes in F4C and BIP families. *Hypotheses*. Profiles of healthy change in RF and ER will mediate the treatment effect of F4C over BIP on: (3a) FV (3b) father-child interactions, and (3c) child mental health symptoms (PTSD, internalizing/externalizing) at post-treatment and at 6- and 12-month follow-ups.

2. **Background:** Describe the background information that led to the plan for this project. **Provide references** to support the expectation of obtaining useful scientific data.

Eighteen percent of children in the United States witness Intimate Partner Violence (IPV) in their homes with significant immediate and long-term consequences to physical and psychological health. Exposure to IPV perpetrated by fathers is common among children referred to child protective services with both national and state level data indicating between 30-40% of child welfare reported children are exposed to IPV, which is most often perpetrated by a father figure. Child protective service systems have long focused on mothers in their interventions for both safety and treatment of IPV. Mothers have been tasked with protecting their children from witnessing IPV or risk losing their children.  Further, all the treatment requirements and opportunities are provided to and expected to be carried out by mothers. Fathers are not held accountable nor are they expected to participate in treatments often due to a belief that interventions do not work for this population. This belief comes from several metaanalyses that report near zero effect sizes of current batterer group intervention programs (BIPs). the only broadly available treatment for IPV perpetrators, in reducing violence. Beyond negligible effects, attrition rates, even for court-mandated programs, are high (30-60%) indicating a significant service need. Importantly, even among intervention completers, recidivism rates for BIPs can be 20-30% indicating high intervention failure.  Often, men who continue to use violence following completion of a group BIP are re-referred to the same program or another similar group program of greater length. Others may serve a short jail sentence with no other treatment provided. Families with IPV are frequently involved with child protective services because it is well known that exposure to IPV is detrimental to children and increases their risk for psychosocial and psychiatric difficulties. (12-14) Despite their ineffectiveness child protective services and the courts in many states continue to use completion of BIPs as sufficient to grant child visitation or as evidence that child protective oversight is no longer needed (15, 16)

**Why focus on fatherhood to engage men?** Given the current "one size fits all" approach to batterer intervention has shown limited impact on the outcome of repeat violence and re-arrest, there is urgent need for alternative intervention approaches. Psychoeducational group interventions have been the standard with the belief they are more effective for the population. They focus on societal influences that condone violence against women, power and control and teach skills for anger management. Evidence suggests that tailoring IPV interventions specifically for men who are fathers may improve outcomes. Indeed, studies suggest fatherhood is a motivator for change among men who perpetrate IPV. Rothman and colleagues 36 found that nearly 2/3 of biological fathers who perpetrated IPV believed that their violence negatively affected their parent–child relationship and many worried about the long-term impact of IPV on their children may be a particularly promising approach. In their study of interparentally violent fathers, Perel and Peled concluded that most fathers desired greater warmth, involvement, and connection in their relationships with their children. Other studies

similarly revealed that men experienced shame, guilt, and remorse when thinking about the harm they may have inflicted upon their children and they report a wish to shield them from their anger. There is evidence that fear of losing family relationships and worry about harm to their children were influential in fathers' decisions to change their behavior and engage in intervention. Therefore, developing IPV interventions that approach men as fathers who can have a positive impact on the health and development of their children rather than as "batterers" could be a more effective way to engage men in treatment leading to better clinical outcomes. Treatment engagement is the first step to intervention success. If individuals do not attend treatment they cannot benefit. Following engagement, to reduce IPV and CM, an intervention must target an appropriate mechanism of change.

What Intervention Mechanisms Could Reduce IPV and CM? Current Batterer Interventions target beliefs about the roles of women and power and control behaviors with limited impact on IPV. Recent research indicates BIPs that more carefully consider psychopathology and psychiatric needs or incorporate mindfulness and psychological flexibility instead of power and control may be more effective in reducing IPV. RF describes the capacity of individuals to understand their own and others' actions as a function of underlying psychological and emotional states and motivations. Individuals with high levels of RF are better able to recognize their own and others' thoughts, emotions, intentions, and desires. Poor RF is associated with increased violent and aggressive behavior and emotional dysregulation. Studies by the PI have indicated fathers with histories of IPV have very low levels of RF. Studies in mothers indicate a significant association between poor RF related to their children and maltreatment. While there is less research on the relationship between paternal RF and child maltreatment, poor RF is a potential core element driving male perpetrated IPV Reading of the larger literature suggests a common and potentially modifiable pathway to IPV and CM through RF. Men at risk for IPV/CM often misperceive threat (acute threat sensitivity) especially from their partners 48 and instead respond to innocuous or ambiguous stimuli with hostility and emotion dysregulation and violence. Lack of RF is important to this chain. Poor RF can result in: 1) misperceptions of partners and children's' intentions or behaviors and 2) lack of understanding of one's own emotions, triggers, thoughts, and behaviors and 3) poor regulation of emotion that can result in violence. The PI has demonstrated low RF in fathers with histories of IPV and experimental studies have indicated that improving emotion regulation reduces violence. Therefore, intervention like F4C that can increase RF could reduce IPV and child maltreatment.

**F4C as an Intervention for IPV and CM:** F4C approaches men through their roles as fathers to increase engagement in the RF focused work that is central to the intervention. F4C is offered individually by master's level therapists to fathers with histories of IPV, defined as threatened or actual sexual or physical violence against an intimate partner in the past 12 months. F4C addresses 9 individually focused core topics, 4 co-parent topics, and 5 father-child focused topics in 60-minute individual therapy sessions over 26 weeks to achieve: (1) reduction of IPV and (2) decreased child maltreatment. In the context of a strong working alliance developed through focus on fatherhood, F4C intervention employs a continual focus on RF and emotion regulation skills. Improvement in these targets in turn leads to reduced IPV and child maltreatment. In concert with the IPV literature. F4C motivates the father to change by continually recognizing his desire to be a better parent and facilitating his ability to reflect on the experiences of his co-parent and children and learn new skills to manage his own affect and thinking to improve outcomes for his family. This is an innovative treatment approach that fills a significant gap in the field of IPV interventions.

Figure 1. Working Theoretical Model of Fathers for Change

Why design an individual approach instead of group? Although programs for both IPV and CM have been implemented using a group approach F4C is an individual treatment approach. We chose this approach because: (1) IPV group approaches have been generally ineffective; (2) there is evidence that antisocial individuals in a group can have a contagion that limits the effectiveness of the group as a whole and may be iatrogenic; (3) interventions for aggressive adolescents were more effective delivered in an individual format compared to group; (4) the therapist needs to understand each client's own childhood history of exposure to violence, hostility triggers, and their intimate relationship patterns to optimally tailor role play, practice reflective functioning, and teach affect regulation skills; (5) our clinical experience with the population raises the concern that some men may be unwilling to share this information in group treatment; and (6) the co-parent and father-child focused components require the therapist to carefully assess RF, emotion dysregulation, and communication patterns based on the type of prior difficulties, whether the couple is still in a relationship, and the developmental age of the children in order to provide appropriate support. This is difficult in group treatment and does not allow for the individualized work and practice in session that is provided in F4C as one-on-one treatment.

